3.4.2 Secondary Efficacy Endpoints and Analyses

Phase 1b

Secondary efficacy endpoints include OR and disease control (DC), duration of stable disease (DSD), best percentage change from baseline of the sum of the longest diameters (SLD) of target lesions and PFS-6.

Phase 2

Secondary efficacy endpoints include duration of response (DoR), time to response (TTR), DC, duration of stable disease (DSD), best percentage change from baseline of the sum of longest diameters (SLD) of target lesions, PFS, and overall survival (OS).

The definitions of these efficacy endpoints and associated analyses are described below. The primary efficacy analyses for the secondary efficacy endpoints will be based on the As-treated Population.

- Disease Control (DC) is defined as a best overall response of confirmed CR, confirmed PR or SD per RECIST v1.1. Disease assessments at Week 16 and 24 for this study are performed on Day 113 (+/- 3 days) and Day 169 (+/- 3 days), therefore the disease control rate at 16 and 24 weeks (DCR-16w and DCR-24w) for this study is defined as the proportion of subjects who achieved a best overall response of confirmed CR, confirmed PR or have SD with duration of SD for a minimum duration of 110 days and 166 days, following the date of randomization for Phase 2 Arm A, B and C subjects or the date of first dose of study treatment for Phase 1b and Phase 2 Arm D and Arm E subjects, respectively. The 2-sided 90% and 95% CIs for DCR-16w and DCR-24w will be estimated using the exact binomial distribution.

- The DoR is defined as the time from the date of first documented response (CR or PR) until the first date of documented progression according to RECIST v1.1 that occurs subsequently after response or death due to any cause, whichever occurs first. For subjects who are alive and progression-free at the time of data cut-off for analysis, DoR will be censored at the PFS censoring time. The DoR will only be evaluated for subjects with an OR and will be calculated using the Kaplan-Meier method.
- TTR is defined as the time from the date of randomization for Phase 2 Arm A, B, and C subjects or the date of first dose of study treatment for Phase 1b and Phase 2 Arm D and Arm E subjects until the first documented OR per RECIST v1.1 and will be evaluated only for subjects with an OR. For subjects proceeding from PR to CR, the onset of PR is taken as the onset of response. TTR will be summarized by treatment group with descriptive statistics.
- DSD is defined as the time from the date of randomization for Phase 2 Arm A, B, and C subjects or the date of first dose of study treatment for Phase 1b and Phase 2 Arm D and Arm E subjects until the first date of documented PD (per RECIST v1.1), or death due to any cause, whichever occurs first. DSD will be analyzed for subjects with SD as their BOR per RECIST v1.1. The median DSD with 90% and 95% CI will be estimated based on the Kaplan-Meier curves. For subjects who are alive and progression-free at the time of data cut-off, DSD will be censored at the PFS censoring time.
- Best percentage change from baseline of the SLD of target lesions per RECIST v1.1 will be derived as the biggest decrease or the smallest increase from baseline on the SLD among all post-baseline disease assessment including unscheduled assessments. Best percentage change from baseline in the SLD of target lesions by subject will be presented in a 'Waterfall' plot, to show each subject's best percentage as a separate bar, with the bars ordered from the largest increase to the largest decrease. Additionally, the percent change from baseline in the SLD of target lesion at each post-baseline disease assessment will be summarized by treatment group with descriptive statistics.
- PFS is defined as in section 3.4.1.2. PFS-9 is the 9-month PFS rate, which is the proportion of subjects who are progression free and alive at 9 months. Similar to PFS-6, Kaplan-Meier curves will be generated for PFS and used to estimate median PFS and the PFS-9 rate along with their 2-sided 90% and 95% CIs.
- Overall survival is defined as the time from date of randomization for Phase 2 Arm A, B, and C subjects or the date of first dose of study treatment for Phase 2 Arm D and Arm E

subjects until death due to any cause. If there is no death reported for a subject by the data cut-off date, OS will be censored at last known alive date. If the last known alive date is after the data cutoff date, OS will be censored at the date of data cutoff for that subject. Kaplan-Meier curves will be generated for OS and used to estimate the median OS and the 1-year survival rate along with their 2-sided 90% and 95% CIs.

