AE = adverse event; BP = blood pressure; CT = computed tomography; D = day; ECG = electrocardiogram; ECOG = Eastern Cooperative Oncology Group; EOI = end of infusion; [REDACTED] LFT = liver function test; [REDACTED] MRI = magnetic resonance imaging; [REDACTED] tic; Q2W = every 2 weeks; Q4W = every 4 weeks; Q12W = every 12 weeks; [REDACTED]; RECIST = Response Evaluation Criteria in Solid Tumors; [REDACTED] SAE = serious adverse event; TSH = thyroid-stimulating hormone; W = week.

Note: On treatment days, evaluations and sample collections should be conducted prior to administration of MEDI4736/tremelimumab unless otherwise indicated. On nontreatment days, all of the pre-treatment assessments will be performed.

- ^a Disease assessments should occur within 7 days prior to dosing.
- ^b If physical examination or safety laboratory tests are performed within 3 days prior to Dose 1, they do not need to be repeated.
- ^c For all treatment arms: Vital signs (temperature, BP, pulse rate, and respiratory rate) will be measured on MEDI4736 and/or tremelimumab treatment days. Vital signs will be measured within 30 minutes prior to the start of tremelimumab and/or MEDI4736 infusion, every 15 minutes (\pm 5 minutes) during tremelimumab and/or MEDI4736 infusion, at EOI of tremelimumab and/or MEDI4736 infusion (\pm 5 minutes), and at 30 and 60 minutes (\pm 5 minutes) post EOI of tremelimumab and/or MEDI4736 infusion. To clarify for subjects receiving combination therapy, vital signs will be measured within 30 minutes prior to start of tremelimumab and MEDI4736 infusion, every 15 minutes (\pm 5 minutes) during tremelimumab and MEDI4736 infusion, at EOI of tremelimumab and MEDI4736 infusion (\pm 5 minutes), and at 30 and 60 minutes (\pm 5 minutes) post EOI of MEDI4736 infusion. For the first day of administration of investigational product, an additional 2-hour (\pm 15 minutes) post EOI period of observation will be required following the 60 minutes (\pm 5 minutes) post EOI assessment of vital signs. For subsequent doses, the additional 2-hour observation period will not be required unless clinically indicated (eg subject experiences an infusion reaction).

^d For all treatment arms: On Day 1 of Week 1, a single ECG will be obtained within 30 minutes prior to start of infusion, within 30 minutes post EOI, and between 2 and 6 hours post EOI of tremelimumab and/or MEDI4736 infusion. To clarify for subjects receiving combination therapy: On Day 1 of Week 1, a

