4.8.3 Efficacy

The efficacy analysis will be based on the As-treated Population. Sensitivity analyses for response-related endpoints (OR, DoR, and DC) will be performed based on the Response Evaluable Population.

The following response-related endpoints and corresponding time-to-event endpoints for primary and secondary efficacy endpoints programmatically-derived from the investigator's assessments or BICR, as well as OS, will be analyzed. More details will be provided in the statistical analysis plan.

- OR is defined as best overall response of confirmed CR or confirmed PR according to RECIST v1.1. The best overall response is defined as the best response (in the order of CR, PR, SD, PD, and not evaluable) among all overall responses recorded from the start of treatment/until progression, or the last evaluable disease assessment in the absence of PD prior to the initiation of subsequent anticancer therapy or discontinuation from the study, whichever occurs first. The best overall response of CR or PR must be confirmed, which means a response of CR/PR is recorded at 1 visit and confirmed by repeat imaging not less than 28 days (4 weeks) after the visit when the response was first observed with no evidence of progression between the initial and CR/PR confirmation visit.
- DoR is defined as the duration from the first documentation of OR to the first documented disease progression according to RECIST v1.1 or death due to any cause, whichever occurs first. For subjects who are alive and progression-free at the time of DCO for analysis, DoR will be censored at the last tumor assessment date. The DoR will be evaluated only for the subjects with an OR.
- DC is defined as confirmed CR, confirmed PR, or SD based on RECIST v1.1. DC at 16 and 24 weeks is defined as a best overall response of confirmed CR, confirmed PR or having SD with duration of SD lasting 16 and 24 weeks, respectively.
- PFS will be measured from the date of randomization or start of treatment until the documentation of disease progression according to RECIST v1.1 or death due to any cause, whichever occurs first. For subjects who are alive and progression-free at the time of DCO for analysis, PFS will be censored at the last tumor assessment date. PFS-6 and [REDACTED] are the proportion of subjects with PFS at 6 months [REDACTED], respectively.

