3.4.1 Primary Efficacy Endpoints and Analyses

Arms A, B, C and E

The two co-primary efficacy endpoints are Objective response (OR) and PFS-6 based on RECIST v1.1.

Arm D

The primary efficacy endpoint is objective response (OR) based on RECIST v1.1.

The primary efficacy analyses for the primary efficacy endpoint(s) will be based on the As-treated Population.

Objective Response

Objective response (OR) is defined as best overall response (BOR) of confirmed CR or confirmed PR according to RECIST v1.1. The best overall response is defined as the best response (in the order of CR, PR, SD, PD, and not evaluable) among all overall responses recorded from the date of randomization for Phase 2 Arm A, B and C subjects or the date of first dose of study treatment for Phase 1b and Phase 2 Arm D and E subjects until progression, or the last evaluable disease assessment in the absence of PD prior to the initiation of subsequent anticancer therapy or discontinuation from the study, whichever occurs first.

The best overall response (BOR) of CR or PR must be confirmed, which means a response of CR/PR is recorded at 1 visit and confirmed by repeat imaging not less than 28 days (4 weeks) after the visit when the response was first observed with no evidence of progression between the initial and CR/PR confirmation visit. A confirmed CR is defined as two CRs that were

separated by at least 28 days with no evidence of progression in-between. A confirmed PR is defined as two PRs or an un-confirmed PR and an un-confirmed CR that were separated by at least 28 days with no evidence of progression in-between. For a subject to qualify for a BOR of SD, at least 54 days from the randomization date or start of treatment date must elapse without disease progression. The definition of 54 days reflects the protocol-defined disease assessment window of ± 3 days (Day 57 plus/minus 3 days).

Subjects who responded with an unconfirmed CR/PR at the time of data cutoff will be reported as CR/PR pending confirmation under the SD category provided the minimum criteria for SD duration (54 days) are met, otherwise this will be reported under the Non Evaluable (NE) category. NE is assigned for a subject who has only a baseline assessment, or a response assessment of CR/PR/SD at an interval of less than 54 days since randomization or the start of treatment and who has no subsequent disease evaluation, or has all overall response evaluations assessed as NE.

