- ≥ 18 weeks (two disease assessment visits plus 2 week visit window to allow for a late assessment) since the last post-baseline evaluable disease assessment, if progression or death occurs prior to end of treatment.
- ≥ 26 weeks (three disease assessment visits plus 2 week visit window to allow for a late assessment) since the last post-baseline evaluable disease assessment, if progression or death occurs after end of treatment.

The details of censoring rules are listed in table 3.4.1-1.

Table 3.4.1-1 Summary of Censoring Guidelines for PFS

Situation	Date of PD/Death or Censoring	PFS Outcome
Documented Progressive Disease (PD)	Date of earliest sign of PD	Event
Death prior to second scheduled post-baseline disease assessment or after ≤1 missed or non-evaluable disease assessment following an adequate post-baseline disease assessments	Date of death	Event
No PD or death at time of analysis or lost to follow-up	Date of last adequate progression-free disease assessment	Censored
Death or PD immediately after ≥ 2 consecutive missed or non-evaluable disease assessments	Date of randomization/the first dose of study treatment or last progression-free disease assessment prior to missed or non-evaluable assessments, whichever occurred last	Censored
Initiation of alternative anticancer therapy before PD or death	Date of last adequate progression-free disease assessment prior to initiation of alternative anticancer therapy	Censored
No tumor assessment at baseline and no death prior to second scheduled post-baseline disease assessment, or no tumor assessment post-first dose	Date of randomization/the first dose of study treatment	Censored

Kaplan-Meier curves will be generated for PFS and used to estimate the PFS-6 along with its 2-sided 90% and 95% CIs. The CIs for PFS-6 will be calculated by applying asymptotic normality to the log-log transformation of PFS-6.

PFS-6 will be compared between the three treatment groups (Arm A, B and C). P-values will be presented without multiplicity adjustment. The comparisons will include the following:

- MEDI4736 + tremelimumab combination therapy (Arm A) versus MEDI4736 monotherapy (Arm B)
- MEDI4736 + tremelimumab combination therapy (Arm A) versus tremelimumab monotherapy (Arm C)

The comparison of PFS-6 will be performed by normal approximation under log-log transformation of Kaplan-Meier estimates of PFS-6 ([Klein et al, 2007](#)).

Specifically, the log HR (1 for combination vs 2 for monotherapy) is estimated as

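### The SAP counts a subject whose progression is first seen at the Week 16 or Week 24 scan as having disease control at that landmark, which inflates DCR-16w and DCR-24w

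*SAP*

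**What the plan says.** SAP 3.4.2 defines DCR-16w and DCR-24w as the proportion with confirmed CR, confirmed PR, or SD of sufficient length. For SD, subjects must "have SD with duration of SD for a minimum duration of 110 days and 166 days" from randomization (Arms A, B, C) or first dose (Phase 1b, Arms D and E). It derives the thresholds from the scan schedule: "Disease assessments at Week 16 and 24 for this study are performed on Day 113 (+/- 3 days) and Day 169 (+/- 3 days").

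The only definition of duration of SD is the DSD item in the same section. It runs "until the first date of documented PD (per RECIST v1.1), or death due to any cause, whichever occurs first", and "DSD will be analyzed for subjects with SD as their BOR per RECIST v1.1". In SAP 3.4.1, the PFS censoring table dates documented progression at the "Date of earliest sign of PD". For a best response of SD, "at least 54 days from the randomization date or start of treatment date must elapse without disease progression".

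Protocol 4.8.3 defines disease control at 16 and 24 weeks as a confirmed response or "having SD with duration of SD lasting 16 and 24 weeks, respectively". On scan timing, footnote a of Protocol Table 4.2.2-1 says "Disease assessments should occur within 7 days prior to dosing".

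The sensitivity analyses in SAP 3.4.4 vary the population, the source of the response assessment and the confirmation of progression. None varies the duration rule.

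**The concern.** The link from the scan windows to 110 and 166 days suggests the intended meaning was SD still present at the landmark scan. Because the duration ends at the date progression is documented, the threshold is also met when that scan shows progression. With on-time scans, DCR-16w then largely measures freedom from progression at the Week 8 scan, and DCR-24w freedom from progression at the Week 16 scan.

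Whether such a subject counts also depends on the exact scan day and on whether a duration is event date minus start date or that plus 1. The SAP does not say which.

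Both rates are named secondary endpoints in Phase 1b and Phase 2, and SAP 3.4.3 repeats them by subgroup. A reader will take them as control at 16 and 24 weeks.

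**Working it through.** **1. The thresholds reproduce.** 113 − 3 = 110 and 169 − 3 = 166. The 54-day minimum for SD is likewise 57 − 3. Each is the earliest on-time scan day.

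**2. One subject.** SD at Day 57 satisfies the 54-day minimum, so best response is SD. Progression is first seen on the Day 113 scan. Duration is 113 − 1 = 112 days, or 113 with the plus-1 convention. Both reach 110, so the subject counts. At Day 169 the duration is 168 or 169, against 166.

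**3. Which scan days count (Week 16; Week 24 is identical).**
- Scans on Days 110–116 (±3 days): progression qualifies on 7 of 7 days with plus 1, and on 6 of 7 without (Day 110 gives 109).
- Scans 0–7 days early, Days 106–113: 4 of 8 days qualify with plus 1 (Days 110–113), and 3 of 8 without.

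**4. Size in closed form.** Inputs: median PFS of 2.86 and 4.40 months (ramucirumab–paclitaxel trial, Protocol 3.2.2) and 6.6 months (SAP 2.4.2). Assumptions: exponential PFS, scans exactly on Days 57, 113 and 169, every event a progression, no confirmed responders. With S(d) = 0.5^(d / (30.4375 × median)), the SAP rule gives S(57) for DCR-16w and S(113) for DCR-24w. Requiring freedom from progression at the scan gives S(113) and S(169). Differences are taken before rounding.

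| Median (months) | S(57) | S(113) | S(169) | Excess 16w | Excess 24w | Subjects of 40 |
|---|---|---|---|---|---|---|
| 2.86 | 63.5% | 40.7% | 26.0% | 22.9 | 14.6 | 9.1 and 5.9 |
| 4.4 | 74.5% | 55.7% | 41.7% | 18.7 | 14.0 | 7.5 and 5.6 |
| 6.6 | 82.1% | 67.7% | 55.8% | 14.4 | 11.9 | 5.8 and 4.8 |

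If only 6 of 7 such progressions count (no plus 1, ±3 days), the 4.4-month DCR-16w is 55.7 + (6/7) × 18.7 = 71.8%.

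**5. Size with scan jitter and deaths.** Simulation of 600,000 subjects per setting: same medians; 8-weekly scans with uniform jitter of ±3 days or 0–7 days early; 0% or 25% of events being deaths dated when they occur; progression dated at the first scan on or after the event; both day counts. The SAP rule required no progression or death by the first scan and a duration of at least 110 (166) days. The comparator was no progression or death on or before the Day 113 (169) scan. Excess in percentage points:

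| Scans | Deaths | DCR-16w | DCR-24w |
|---|---|---|---|
| ±3 days | 0% | 12.5–23 | 10–15 |
| ±3 days | 25% | 10–18 | 8–11 |
| 0–7 days early | 0% | 6–12 | 5–8 |
| 0–7 days early | 25% | 4–9 | 3.5–6 |

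The excess was upward in all 24 settings. At a median of 4.4 months, with no deaths and no plus 1, the rates are 72% against 56% and 54% against 42% with ±3-day scans. With early scans they are about 65% against 57% and 48% against 43%. Of progressions first seen at the landmark scan, 86–100% count with ±3-day scans and 39–52% with early scans, in line with step 3.

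**The case against.** The strongest reply is that the protocol defines a duration, not a scan result. Progression on Day 113 is 112 days after Day 1, which is exactly 16 weeks, so the SAP rule is generous but does not contradict the protocol. That is correct. The excess is measured against progression-free status at the scan, which is a choice of comparator, though it is what the endpoint's name conveys.

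Second, 3.4.2 does not cross-refer from duration of SD to DSD, and details may sit in the statistical programming plan or in redacted text. But DSD is the only definition in the visible SAP, and none of the visible text excludes these subjects.

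Third, the two effects do not peak together. With ±3-day scans the excess is largest but scan day hardly matters. With early scans scan day matters but the excess roughly halves. This stands, so the upper figures need on-time scans, no deaths and the shortest median.

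Fourth, the documents' own gastroesophageal monotherapy data are much lower: DCR-12w of 25% (7/28, Protocol 3.2.3) and DCR-24w of 15% (Protocol 1.5). An exponential through 25% at 12 weeks predicts 0.25² = 6% at 24 weeks, so that curve does not fit both points. A constant hazard between them, ln(25/15)/12 = 0.0426 per week, gives about 29.6%, 21.1% and 15% at Weeks 8, 16 and 24. The 8-week drops are about 8.5 and 6 points before allowing for deaths or early scans. These figures come from different data cuts and denominators, but they suggest the lower half of the range may be more realistic, at least for monotherapy.

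Fifth, the simulation has no censoring. A subject whose last evaluable scan is stable and falls just before Day 110 or 166 is wrongly excluded. This opposite error is confined to that group, but its size was not estimated.

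Finally, DCR is descriptive, no between-arm test of it is planned, and Kaplan–Meier PFS is reported alongside. That limits the consequence but does not correct the two rates.

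**Conclusion.** The concern holds. As written, SAP 3.4.2 credits disease control at 16 or 24 weeks to subjects whose progression is first documented on that scan. The overall excess is 4 to 23 points for DCR-16w and 3.5 to 15 for DCR-24w. In 40 Arm E subjects this is 40 × 0.04 to 40 × 0.23, about 2 to 9 subjects, and 40 × 0.035 to 40 × 0.15, about 1 to 6.

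The documents give no DCR planning rate, so these figures rest on the assumed PFS curve and 8-weekly scans. Confirmed responders count under either rule and would reduce the excess, mainly at 24 weeks. If programmers require the scan showing SD itself to fall at 54 days or later, the early-scan DCR-16w excess shrinks; DCR-24w does not change. The direction does not depend on the median, the day count, the scan window or the share of deaths examined. The point should be fixed, but it does not reach the co-primary endpoints.

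**What to change.** Define DCR-16w (DCR-24w) as confirmed CR or PR, or SD with an evaluable non-PD assessment at the scheduled Week 16 (Week 24) scan or later and no PD or death on or before that scan. This keeps the protocol's treatment of confirmed responders, who have no duration condition. Reconcile the SAP's ±3-day window with the protocol's 7 days before dosing, and apply the same window to the 54-day SD minimum. State whether durations are event date minus start date or that plus 1.

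The cost is SAP wording and one re-derivation from data already collected. The reported rates will be less favourable. A change at SAP version 3.0 in an open-label study is late, so if the SAP is already final, report the current rule alongside as a supportive analysis.

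### DoR and duration of SD run to death after a therapy switch or missed scans where PFS is censored, which may credit unsupported time to DCR-16w and DCR-24w

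*SAP*

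**What the plan says.** **DoR (SAP 3.4.2).** It runs from first response to the first documented progression "that occurs subsequently after response or death due to any cause, whichever occurs first". The censoring sentence covers survivors only: "For subjects who are alive and progression-free at the time of data cut-off for analysis, DoR will be censored at the PFS censoring time".

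**DSD (SAP 3.4.2).** It runs from randomization or first dose "until the first date of documented PD (per RECIST v1.1), or death due to any cause, whichever occurs first". Its censoring sentence has the same restriction: "For subjects who are alive and progression-free at the time of data cut-off, DSD will be censored at the PFS censoring time".

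**PFS (SAP 3.4.1 and Table 3.4.1-1).** For the situation "Initiation of alternative anticancer therapy before PD or death", PFS is censored at "Date of last adequate progression-free disease assessment prior to initiation of alternative anticancer therapy". Progression or death straight after two or more missed or non-evaluable assessments is also censored at the last progression-free assessment before the gap. The gap is 18 weeks or more on treatment and 26 weeks or more after end of treatment. Neither rule depends on whether the subject is alive at cut-off.

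**DCR-16w and DCR-24w (SAP 3.4.2).** A subject counts with a confirmed CR, a confirmed PR, or if they "have SD with duration of SD for a minimum duration of 110 days and 166 days", respectively. The two limits come from the scans due on Day 113 and Day 169, each with a 3-day window. A best response of SD needs 54 progression-free days, and best response uses only assessments before subsequent therapy (SAP 3.4.1).

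**Follow-up (Protocol 4.2.3).** After a switch of therapy, follow-up visits are no longer required but survival follow-up continues.

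Protocol 4.8.3 does not close the gap. It restricts DoR censoring to the same survivors and says only that SD must last 16 or 24 weeks.

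**The concern.** A subject who has switched therapy or missed scans and then died is outside the DoR and DSD censoring sentences. No other censoring rule is stated, so both durations run to the death date. PFS for the same subject stops at the last adequate scan. Progression documented after a switch or a long gap is treated in the same inconsistent way.

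Two things are at stake. First, DoR and PFS can disagree on event status and time in the same responder. Second, if DSD is the duration used for DCR-16w and DCR-24w, time on the next therapy, or time with no scan, can be credited to study drug, and the credit depends on the subject having died.

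The follow-up plan makes the pattern likely: after a switch, deaths are still captured while scans usually are not. The second-line median survival figures cited in Protocol 3.2.2 run from 3.6 to 9.63 months, so deaths between a switch and cut-off should be expected.

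**Working it through.** **1. The SAP's own day counts reproduce.** Minimum SD: 57 − 3 = 54 days. DCR-16w: 113 − 3 = 110. DCR-24w: 169 − 3 = 166. Missed-assessment gaps: 2 × 8 + 2 = 18 weeks (126 days) and 3 × 8 + 2 = 26 weeks (182 days).

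**2. The literal rules applied to example subjects.** All have SD on Day 57 as the last scan. The last column assumes that duration of SD means DSD.

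| Subject | PFS | DSD as written | DCR-24w (≥ 166 days) |
|---|---|---|---|
| A. Switch Day 80, death Day 200, before cut-off | Censored Day 57 | Event Day 200 | Counts |
| B. Switch Day 80, alive at cut-off | Censored Day 57 | Censored Day 57 | Does not count |
| C. No switch, scans on Days 113 and 169 missed, death Day 190 on treatment | 190 − 57 = 133 ≥ 126: censored Day 57 | Event Day 190 | Counts |

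A and B differ only in that A died. With a last scan on Day 57, the missed-scan conflict begins with deaths on Day 57 + 126 = 183 (on treatment) or Day 57 + 182 = 239 (after end of treatment).

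**3. Would aligning DSD with PFS be enough?** Subject D has a last scan on Day 57, no switch, and dies on treatment on Day 170. The gap is 170 − 57 = 113 days, below 126, so PFS is an event on Day 170. Aligned DSD is also 170 days, and 170 ≥ 166, so D still counts in DCR-24w on one scan. After end of treatment the same holds for deaths up to Day 238. Alignment cures A and C but not D.

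**4. Size per subject.** In Arm E, 1/40 = 2.5 points. Take 6/40 = 15% as an illustrative base, matching the DCR-24w cited for MEDI4736 monotherapy in Protocol 1.5. The exact (Clopper-Pearson) 90% intervals below use a method that reproduces SAP Table 2.4.2-2 (10/36: 16% to 43%; 14/36: 25% to 54%). The number of extra subjects is assumed.

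| Extra subjects | DCR-24w | 90% CI |
|---|---|---|
| 0 | 15% | 7% to 27% |
| 1 | 17.5% | 9% to 30% |
| 2 | 20% | 10% to 33% |
| 4 | 25% | 14% to 39% |

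**5. Size under assumed switching.** These inputs are assumptions, not in the documents: 20-40% of subjects have SD at Day 57; 15-35% of those switch without RECIST progression, uniformly over Days 60-150; survival after the switch is exponential with median 3-5 months. The 7-month cut-off is the minimum follow-up in Protocol 4.8.1; 19 months is assumed.

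Inflation in points = 100 × P(SD) × P(switch) × f, where f is the share of switchers who die on or after Day 166 and before cut-off. Their last scan before the switch is always earlier than Day 166. The multiplier is 100 × 0.20 × 0.15 = 3 at the low end and 100 × 0.40 × 0.35 = 14 at the high end.

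| Cut-off after start | f (median 3 / 5 months) | DCR-24w inflation |
|---|---|---|
| 7 months | 0.193 / 0.147 | 3 × 0.147 = 0.4 to 14 × 0.193 = 2.7 points |
| Uniform, 7-19 months | 0.491 / 0.463 | 3 × 0.463 = 1.4 to 14 × 0.491 = 6.9 points |
| 19 months | 0.613 / 0.646 | 3 × 0.613 = 1.8 to 14 × 0.646 = 9.0 points |

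For DCR-16w with the uniform cut-off the range is 1.1 to 5.9 points. The missed-scan route is not included. The inflation grows with follow-up, although a 24-week rate should be settled once every subject has passed 24 weeks.

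**6. DoR.** A simulation with 10 responders, of whom 15-35% switch, gives a difference in median DoR between the two rules of about 0 to 2 months.

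**The case against.** **The DCR consequence is an inference.** The DCR sentence speaks of a duration of SD without citing DSD, and it derives its limits from the Week 16 and Week 24 scans. It can be read as SD lasting to those scans, and best response is already limited to assessments before subsequent therapy. On that reading subject A fails DCR-24w. A reader might conclude that the SAP definitely scores a death after a switch as disease control; the text does not settle that. What stands is that DSD is the only duration of SD defined in the visible SAP, and a programmer following it literally would count subject A.

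**The sponsor may have meant the whole PFS table to apply.** The PFS prose also opens with a sentence about living subjects, and its new-therapy rule appears only in the table. That intent is plausible, but 3.4.2 does not state it.

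**Counting deaths after a switch in DoR is defensible in itself.** This stands. For DoR the issue is only inconsistency with PFS. A reader might infer that DoR also raises DCR; it cannot, because a confirmed CR or PR counts whatever its duration.

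**The affected subjects need not have had just one scan.** A reader might infer that their SD was never seen after Day 57. In the scenarios above, about 46-50% of the subjects who raise DCR-24w switched after Day 113, so they would have had a Week 16 scan.

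**The size rests on assumed inputs.** This also stands. At the low end with a 7-month cut-off it is under one subject in 40.

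**Conclusion.** The inconsistency is in the stated rules: for a subject who switches therapy or misses two or more assessments and then dies, DoR and DSD can have an event at death where PFS is censored. The effect on DCR-16w and DCR-24w is conditional on DSD being the duration used. Given that, each affected subject is worth 2.5 points in Arm E, and the assumed switching scenarios give about 0.4 to 9 points for DCR-24w. The documents give no count of such subjects, so this is a range of possibilities and not an estimate.

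A reader might take this to threaten the main result. It does not: ORR and PFS-6 are unaffected, and no test or decision rule in the visible text uses DCR or DoR. It is still worth correcting, because the rule can score a subject who dies above an otherwise identical survivor, the DCRs and DoR are also reported in small subgroups (SAP 3.4.3), and the data needed are already collected.

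**What to change.** Two changes to SAP 3.4.2, both needed:

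1. State that the end date and the event or censoring status of DoR and DSD are those given by Table 3.4.1-1 for every subject, alive or dead at cut-off. If the new-therapy row of that table is ever changed, PFS, DoR and DSD should change together.
2. State that SD counts towards DCR-16w or DCR-24w only if an evaluable progression-free assessment on or after Day 110 or Day 166, respectively, and before any subsequent anticancer therapy, supports it. Step 1 alone would still credit deaths less than 18 weeks (on treatment) or 26 weeks (after end of treatment) after the last scan, as subject D shows.

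The cost is one or two SAP sentences and a programming change, with no new data. DCR-16w and DCR-24w may come out slightly lower.
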